## Aim 1. Evaluate differences in infant health when diaper changes occur at 3- versus 6-hours?

**RQ1**. What caregiving activities other than diaper changes are included in bundled care events and do they differ when diaper changes are bundled every 3 versus 6 hours **Analysis:** Each day bundled care is observed, a list of activities will be marked as occurred (1) or did not occur (0). Each infant will have 18 days of data denoting whether an activity occurred or did not occur. Hierarchical clustering of repeated data with an appropriate algorithm that

or did not occur. Hierarchical clustering of repeated data with an appropriate algorithm that producing stable and accurate clusters will be used will be to determine the groupings of activities that occur in the sample. The frequency of the clusters between the intervention groups will be compared.

**RQ2**. Does infant physiological stability ( $\Delta$  heart rate,  $\Delta$  respiratory rate,  $\Delta$  oxygen saturation, # apnea # bradycardias, # desaturations, feeding tolerance) differ between 3- and 6-hour bundled care diapering?

**Analysis:** Heart rate, respiratory rate and oxygen saturation values captured a minute apart for each observed bundled care with a diaper change will be graphically displayed in various constructions to be able to compare the general trends of change in these outcomes between intervention groups, among periods of the bundled care (before, during and after) and over weeks. Further, we will create a daily average of each outcome by period (before, during, and after). Using a repeated measures analysis, we will test for difference among the periods and intervention group and all pairwise period comparisons between groups. PMA and infant illness severity (Technology Burden Score) will be used as a covariate. We will control for multiple comparisons.

A Poisson Generalized linear model for repeated measure will be use to estimate the daily number of apnea, bradycardias, and desaturations events over the 18 days of bundled care observations with a diaper change. The need for a random intercept or slope will be assessed.

 $Log(\# of Apnea Events_{ij}) = b_0 + b_1[I(6HrBC_i)] + b_2(Day_{ij}) + b_3[(I(6HrBC_i)) \times (Day_{ij}) + b_4(PMA_{ij}) + b_5(TechBur_{ij}),$ 

where  $Log((\# of Apnea Events_{ij}))$  is the logarithm of the number of apnea events for individual i at day j.  $b_0$  is the mean log of apnea events for participants who receive 3-hour diaper changes

and are mean postmenstrual age and with mean technology scores at the start of the study;  $b_1$  is the change in log number of apnea events for those receiving 6-hour diaper changes;  $I(6HrBC_i)$  is an indicator for participants receiving bundled care and 6-hour diaper changes;  $b_2$  is the change in log of the number of apnea events for each day of bundled care;  $Day_{ij}$  is the indicator of the day the number of apnea events was recorded;  $b_3$  is the additional change in log of the number of apnea events over days for those receiving bundled care and 6-hour diaper changes;  $PMA_{ij}$  is the difference from the baseline mean postmenstrual age of the ith participant at the jth day;  $TechBur_{ij}$  is the difference from the baseline mean technology burden score for the ith participant at the jth day;  $b_4$  and  $b_5$  are the expected changes in log number of events for postmenstrual age and technology burden scores, respectively. The estimate of interest is  $b_3$ . The feeding tolerance outcome will be estimated in a similar manner using the appropriate distribution of the outcome and link function for the model.

**RQ3**. Does infant weight gain over time differ between 3- and 6-hour bundled care diapering? **Analysis:** The trajectories of weight measured across the 18 days of bundle care will be fitted using a linear mixed model with a random intercept. We will first determine the best trajectory fit for weight over the 18 days. Once we select an appropriate trend for the data a model similar to the one described below will be estimated.

$$Weight_{ij} = b_0 + b_{i0} + b_1[I(6HrBC_i)] + b_2(Day_{ij}) + b_3[(I(6HrBC_i)) \times (Day_{ij}) + b_4(PMA_{ij}) + b_5(TechBur_{ij}) + \\ \epsilon_{ii},$$

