d. Procedures: A neonatal provider will give approval for participation in the study. Parents will be approached for consent after eligibility screening is completed (≤ 32 weeks gestation). The principal investigator is a clinical nurse specialist and nurse scientist who has been affiliated in the Intensive Care Nursery since 1993. Study personnel will explain the study, allow time for questions, have a parent sign the consent form, and a copy will be given to the parent. Parents will provide consent for their infant's participation in the study and will give permission for themselves to participate in an interview about the study, if selected. Five parents from each group will purposively selected to participate in an interview. Parents will be selected to include parents with infants < 1000 grams at birth and parents with infant ≥ 1000 grams at birth.

[figure not shown]
Following consent, the infant will be monitored until all inclusion and exclusion criteria are met. At that time randomized to an intervention group and data collection will be initiated. The intervention will continue for six weeks at which time collection of data will stop and bundled diapered care will resume according to unit protocol. If the infant no longer meets inclusion criteria the intervention will be discontinued and routine data collection will be discontinued. The exclusion criteria will be noted, e.g. use of diaper cream, and data collection regarding any new illness characteristics or treatments will continue. If an infant requires a diaper change due to a stool or other needed procedure this will be recorded on a bedside card.

Ten nurses will be recruited for participation in interviews around intervention acceptability at the end of the study.

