**Table 1. Data Collection** 

Construct	Measure/	Variable	Time frame		
	Instrument				
	Descriptive data to describe the sample				
Maternal history	EMR 	Age, medical hx. of skin disease,	Enrollment		
Infant characteristics	EMR	GA  , birth weight, diagnoses, antibiotics, delivery mode, lab values as required to describe skin health (e.g. albumin, protein, bilirubin) All bundled care event time frames from study entry to study discharge (expected vs. actual bundled times) During bundled care—respiratory support, changes in support, FiO 2 changes, average Daily FiO 2 , caffeine	Enrollment, 3x/week, or as available		
	Aim 1. Infant	Health			
Bundled care	Observation, videotape & EMR	Specific interventions (e.g. suctioning, positioning, offering pacifier, diapering) Length of bundled care events Time between bundled care events	Observer 3x/week for the 3-hour diaper group and 4s/week for the 6-hour group to allow for one within group comparison; Videotaped 1x/week Daily; retrieved 3x/week		
Physiologic stability	GE monitor	1-minute values of heart rate, respiratory rate and oxygen saturation 15 minutes before and after each observed bundled care event	3x/week for the 3-hour diaper group and 4s/week for the 6-hour group to allow for one within group comparison		
	EMR	# bradycardia events daily	Daily; retrieved 3x/week		
	EMR	# apneic events daily	Daily retrieved 3x/week		
	EMR	# desaturation events daily	Daily retrieved 3x/week		
	EMR	Feeding tolerance (emesis, gastric residual volumeml, feeding interruptions)	Daily retrieved 3x/week		
Weight gain	EMR	Daily weight in grams	Daily retrieved 3x/week		
	Aim 1. Covariates				
Development	EMR	Postmenstrual age (PMA)			
Severity of illness	Technology Burden	Total Score 0-100	Retrieved 3x/week to coincide with observation		
	EMR	Time in minutes since the end of the last bundled event	With each observation		

	Aim 2. Skin Health (buttocks and chest)			
Acid mantle	рН	0.00 to 14.00.	3x/week with observation	
development				
Water loss	TEWL	TEWL 	3x/week with observation	
	Dermalab			
Skin status	NSCS⁴	NSCS-range 3-9	Twice daily retrieved	
			3x/week	
Microbiome		Microbiota pattern	3x/week with observation	
	Aim 2. Covariates			
	EMR	PMA		
	EMR	Delivery mode		
	EMR	Time since last bath	3x/week with observation	
	EMR	Daily urine output	3x/week with observation	
	EMR	Time in minutes since the last bundled event		

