	EMR	Stool pattern (categorical)	3x/week with observation	
	EMR	Feeding type (formula vs. breast and route; enteral	3x/week with observation	
		vs. nipple)		
	Bedside	Diaper size and brand	3x/week with observation	
	checklist			
	Stool	Scavenged	1x/week as available	
	Aim 3. Feasibility			
Intervention	Interviews	Parent perceptions	End of infant data	
acceptability			collection;	
and feasibility		Provider perceptions	At study end	
•	Exploratory Health Outcomes			
Late onset	EMR	Presence or absence	Two weeks after end of the	
sepsis			study	
Urinary tract	EMR	Presence or absence	Two weeks after end of the	
infection			study	

<sup>1EMR=electronic medical record; GA=gestational age at birth; TEWL=transepidermal water loss; NSCS=neonatal skin condition score.

- ii. Physiologic measures: Heart rate, respiratory rate, and pulse oximetry will be measured continuously with a GE Cardiopulmonary monitor (standard monitor at DUH) with acquisition from the server, sent to the PI weekly for all enrolled subjects in a data secured zip file. 1-minute values for each 24-hour observation in which a bundled care data collection occurred will be extracted and the required time frames will be extracted for analysis.
- iii. Bundled Care: The content of bundled care will be determined through the observational coding of all caregiving activities during weekly observations (3 times/week for 3-hour diapered and 4 times/week for the 4-hour diapered intervention group; see intervention section above) and 12-hour videotaping (1 time per week for each group) of bundled care events. The length of time for each bundled care event will be operationally defined as beginning when the nurse's hands enter the incubator and will end when the nurse's hands leave the incubator following caregiving.
- iv. Microbiome: One microbiome sample will be taken from the buttocks immediately after the diaper is removed and before the skin is cleaned, if there is NO stool present. A second swab will be collected from the chest at the same time. The following procedure will be used for all microbiome samples. Needed supplies will include a tube of sterile solution of PBS + 0.1%Tween 20 and a Nova Biostorage FLOQ swab with cuvette.
  - a. Remove the swab from the package
  - b. Insert the tip of the swab into the sterile PBS + 0.1% Tween 20 solution until moistened.

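### Aim 1 RQ1 draws on observed bundles that over-represent diaper changes in the 6-hour arm, and Section 10 does not name the weekly video that could correct this

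*Combined protocol and SAP*

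**What the plan says.** - **Sources (Section 4.e).** For the specific interventions in a bundle, Table 1 lists "Observation, videotape & EMR", at this frequency: "Observer 3x/week for the 3-hour diaper group and 4s/week for the 6-hour group to allow for one within group comparison; Videotaped 1x/week". The bundled care paragraph (4.e.iii) reads: "The content of bundled care will be determined through the observational coding of all caregiving activities during weekly observations". It then adds a second source: "12-hour videotaping (1 time per week for each group) of bundled care events". That paragraph labels the arm observed four times a week as a 4-hour group, while Table 1 labels it the 6-hour group. The two must be reconciled; the counts below use Table 1's label.
- **Analysis (Section 10, Aim 1 RQ1).** One 1/0 activity list is scored per observed day. "Each infant will have 18 days of data denoting whether an activity occurred or did not occur". Activities are grouped by hierarchical clustering, and then: "The frequency of the clusters between the intervention groups will be compared". Bundle type (with or without a diaper change) is not a factor, and video is not mentioned here or anywhere else in Section 10.
- **Which bundles are observed (Section 10, Aim 1 RQ2 and RQ4).** RQ2 describes the 18 observation days as days with a diaper change. RQ4 adds, on one randomly chosen day a week in the 6-hour arm, the bundle without a change, for comparison with the change bundle of the same day.
- **Delivered care (Section 4.c and 4.d).** Infants in the 6-hour arm keep 3-hourly care for everything except the diaper. At the off interval the nurse checks for stool, changes the diaper if there is any, and notes the deviation. On duration: "The intervention will continue for six weeks at which time collection of data will stop".

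**The concern.** In the 3-hour arm every scheduled bundle includes a diaper change, so a sample of change bundles represents the care given. In the 6-hour arm only every second scheduled bundle does. An observation plan centred on change bundles is therefore representative in one arm and not in the other.

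The no-change bundle is also where a difference between arms is most likely to appear. If other activities drop out when the diaper is left alone, or move to the change bundle, comparing mostly change bundles with change bundles will understate it. The background section gives the study's purpose as limiting optional, stressful handling. Whether the no-change bundle holds less handling, or the same handling minus the diaper, is central to that purpose.

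**Working it through.** **Inputs.** Observers: 3 a week (3-hour arm), 4 a week (6-hour arm). Video: 12 hours once a week in both arms (Table 1 and 4.e.iii). Duration: 6 weeks (4.d). Bundles every 3 hours, diaper change due every 6 hours (4.c). Not given, so assumed: the frequency of an activity in change bundles (p_c) and no-change bundles (p_n), and the share q of off-interval bundles in which stool triggers a change.

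**1. The plan's 18.** 3 × 6 = 18, which reproduces the figure. Adding a separate video day each week would give (3 + 1) × 6 = 24.

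**2. Observed mix, 6-hour arm.** 18 change bundles and 6 no-change bundles: 18/24 = 75% if the extra bundle counts as its own unit. If it is reserved for RQ4, 18/18 = 100%.

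**3. Scheduled mix.** (24/6)/(24/3) = 4/8 = 50%.

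**4. Shift in the 6-hour arm's activity frequency.** Observed minus scheduled is (0.75 − 0.50) × (p_c − p_n) for the 75% mix and (1.00 − 0.50) × (p_c − p_n) for change bundles only.

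| p_c, p_n (assumed) | Scheduled mix | 75% mix | Shift at 75% | Shift at 100% |
|---|---|---|---|---|
| 60%, 50% | 55% | 57.5% | 2.5 points | 5 points |
| 70%, 40% | 55% | 62.5% | 7.5 points | 15 points |
| 80%, 30% | 55% | 67.5% | 12.5 points | 25 points |

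**5. Effect on the between-arm difference.** Assume change bundles have the same content in both arms, so the 3-hour arm shows p_c. The true difference on schedule is 0.50 × (p_c − p_n). The 75% mix shows 0.25 × (p_c − p_n), which is half. Change bundles alone show zero.

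**6. Stool-triggered changes.** Assume these bundles resemble scheduled change bundles. The delivered share of change bundles becomes 0.5 + 0.5q, and the true difference becomes 0.5(1 − q) × (p_c − p_n). The share lost at the 75% mix is 1 − 0.25/[0.5(1 − q)]:

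- q = 0: 50%
- q = 10%: 44%
- q = 25%: 33%
- q = 50%: 0%

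With change bundles only, the loss stays total in each of these cases.

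**7. What the video holds.** 12/3 = 4 consecutive bundles a session, × 6 weeks = about 24 per infant, about 12 with a scheduled change and 12 without. Unweighted pooling with the observer bundles would not restore the mix: (18 + 12)/(24 + 24) = 62.5% change bundles.

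**The case against.** **Video is not excluded.** Sections 4.e and 4.e.iii make it a source for bundle content, RQ1 does not rule it out, and a video session could fall on an observer day. A reader might infer that the plan discards the video. The documents do not say so: the inference rests on 18 = 3 × 6 and on Section 10's silence. What stands is a gap between the data collection text and the analysis text.

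**RQ1 scores days, not bundles.** The 75% figure treats the extra bundle as a separate unit, which RQ1 does not state. If it is left out, the share is 100%. If it is merged into that day's list, the result is different again: at an assumed 80% and 40%, with independent bundles, the 6-hour arm would show (2 × 0.80 + 0.88)/3 = 0.83, where 0.88 = 1 − 0.2 × 0.6. The scheduled mix gives 0.60. This objection is correct about the unit, but none of the three readings removes the over-representation of change bundles.

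**The gap may be small.** Section 4.c says that only the timing of the diaper change differs, so large gaps in other activities would depart from the design. That is fair, and it is why the range starts at 2.5 points. But whether other activities differ is the question RQ1 asks, so a gap of zero cannot be presumed.

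**Descriptive summaries are already planned.** Section 10 opens with means and proportions by group, which could cover each activity. Unless bundles are labelled, those summaries carry the same mix.

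**Some no-change bundles are observed.** A reader might infer that the trial could not tell whether 6-hour diapering reduced handling or only rearranged it. That goes too far. Six no-change bundles per infant, about 6 × 25 = 150 in the arm, could be separated or weighted if lists are kept per bundle. Nor do the documents support dropping the observer data.

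**Conclusion.** The concern holds as a mismatch between the bundles RQ1 observes and the care it is meant to describe, in the 6-hour arm only. Change bundles make up 75% or 100% of the observed bundles, depending on a point the plan leaves open, against 50% on schedule. A true between-arm difference in a non-diaper activity is about halved in the first case and lost in the second.

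This rests on two assumptions: that change bundles have similar content in both arms, and that stool-triggered changes are uncommon. The loss at 75% falls as such changes become more frequent and disappears at about half of off-interval bundles. The size in percentage points cannot be fixed from the documents, because the gap between bundle types is unknown. The figure of 24 video bundles assumes six full weeks and close to 3-hourly timing; the 75% share does not depend on the number of weeks.

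**What to change.** In Section 10, Aim 1 RQ1:

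1. Make the bundle the unit of analysis and label each one as with or without a diaper change. State whether the fourth weekly observation in the 6-hour arm enters RQ1.
2. Bring the video-coded bundles into the between-arm comparison, or weight the two observed bundle types to the delivered mix. The recorded bundle times and the bedside record of unscheduled changes can supply that mix. If video and observer bundles are pooled, weight by bundle type and count a bundle captured by both sources once.
3. Compare each non-diaper activity by arm in a mixed model with an infant random intercept (logistic, since activities are scored 1 or 0). Report estimates with confidence intervals, which suits the stated aim of estimating values and variances for a larger study.
4. Keep the hierarchical clustering as description.

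The cost is SAP wording and more analysis work; the video is already planned. If the between-arm estimate rests on video alone, there are about 6 sessions per infant in place of 18 observer days, though each holds about four bundles. The change should be fixed before the data are examined.

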## **Research Summary**

NCT03370757

- 1. **Protocol Title** Very Low Birth Weight (VLBW) Preterm Infant Health Outcomes with Bundled Care in the Neonatal Intensive Care Unit: A RCT
- 2. Purpose of the Study Explore the impact of bundling nursing care activities on the overall health of VLBW preterm infants who receive bundled care in a Level IV Neonatal Intensive Care Unit (NICU). Specific study aims include:
  - **Aim 1.** Evaluate differences in infant health when diaper changes occur at 3- versus 6-hours during 3-hour bundled care.
    - **RQ1.** What caregiving activities other than diaper changes are included in *bundled care events* and do they differ when diaper changes are bundled every 3 versus 6 hours.
    - **RQ2.** Does infant physiological stability ( $\Delta$  heart rate,  $\Delta$  respiratory rate,  $\Delta$  oxygen saturation, # apnea # bradycardias, # desaturations, feeding tolerance) differ **between 3- and 6-hour bundled care diapering**?
    - **RQ3.** Does infant weight gain over time differ between 3- and 6-hour bundled care diapering?
    - **RQ4.** Within the 6-hour bundled diaper care group, does infant physiological stability ( $\Delta$  heart rate,  $\Delta$  respiratory rate,  $\Delta$  oxygen saturation) differ between bundled care with and without a diaper change (3 versus 6-hours)?
  - **Aim 2.** Evaluate differences in infant skin health between 3- and 6-hour bundled care diapering at two sites (buttocks and chest).
    - **RQ1.** Does skin transepidermal water loss (TEWL) differ over time and at the end of 6 weeks between 3- and 6-hour bundled care diapering on the chest and buttocks?
    - **RQ2.** Do neonatal skin condition scores differ over time and at the end of 6 weeks between 3- and 6-hour bundled care diapering?
    - **RQ3.** Does skin pH differ over time and at the end of 6 weeks between 3- and 6-hour bundled care diapering?
    - **RQ4.** Does the skin microbiota differ over time and at the end of 6 weeks between 3- and 6-hour bundled care diapering?
  - **Aim 3.** Evaluate the acceptability and feasibility of conducting a bundled care intervention where the frequency of one care activity, diaper care, is standardized.
    - **RQ1.** What are the perceptions of parents and providers about the criteria necessary for conducting a diaper change in the NICU?
    - **RQ2.** What are the perceived barriers of parents and providers to longer timeframes between diaper changes?

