### 10. Data Analysis and Statistical Considerations

Initially, we will conduct descriptive analyses, including examination of means and proportions and the measures of variability for each variable overall and by bundled care groups. The descriptive analyses will be followed by modeling approaches to respond to the research questions. Tests of statistical significance will be two-sided and the threshold for statistical significance will be P < 0.05.

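### RQ1 of Aim 1 asks whether individual caregiving activities differ between arms, but its analysis compares only data-derived clusters and gives no per-activity arm difference with an interval or test

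*Combined protocol and SAP*

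**What the plan says.** Section 2 (Aim 1, RQ1) asks what the bundle contains besides the diaper change and "do they differ when diaper changes are bundled every 3 versus 6 hours". Section 10 repeats the question before the RQ1 Analysis: "What caregiving activities other than diaper changes are included in bundled care events and do they differ when diaper changes are bundled" every 3 or 6 hours.

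The data are binary and repeated: "Each infant will have 18 days of data denoting whether an activity occurred or did not occur". The method begins "Hierarchical clustering of repeated data with an appropriate algorithm that" is meant to give stable and accurate clusters, and these define the groupings of activities in the sample. The comparison of arms is then one sentence: "The frequency of the clusters between the intervention groups will be compared". The RQ1 text names no test, model, number of clusters, handling of repeated days or multiplicity rule.

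The opening of Section 10 plans a descriptive step, "including examination of means and proportions and the measures of variability for each variable overall and by bundled care groups", and says that modelling to answer the research questions follows it. It also sets the general rule: "Tests of statistical significance will be two-sided and the threshold for statistical significance will be P < 0.05".

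**The concern.** The question is about activities, while the comparison is about clusters. A change in one activity, suctioning for example, is spread over several clusters if days are clustered, or averaged with its neighbours if activities are clustered. A null result on cluster frequency would therefore be weak evidence that no single activity changed, and a positive result would not by itself identify the activity.

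This affects how the rest of Aim 1 is read. Section 4c states as a design feature that the arms differ only in when the diaper is changed. The documents do not label RQ1 as a check on that, but it is the only research question whose data could show whether other care moved or dropped out along with the diaper change. Section 4b gives the study's goal as estimating values and variances for a larger trial. A per-activity difference with an interval can be carried forward to that trial; the frequency of a cluster found in this sample transfers poorly.

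**Working it through.** **Inputs from the documents.** At least 25 infants per arm with complete data (Section 4b); 18 observed days per infant (3 per week × 6 weeks); two-sided 0.05. Table 1 lists activities only as examples. No number of activities, base rate, within-infant correlation, effect size or number of clusters is given. The documents state no power figure for RQ1, so there is none to reproduce.

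**Step 1: closed form (normal approximation).** Assumptions: activity rate 0.5, a 15-point arm difference in one activity, within-infant correlation ρ from 0.05 to 0.30, eight activities, four clusters, and three uncorrelated activities in the affected cluster.

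- Variance of an infant's proportion: V = 0.25/18 × (1 + 17ρ). For ρ = 0.05, V = 0.0257; for ρ = 0.30, V = 0.0847.
- SE of the arm difference: √(2V/25) = 0.0453 and 0.0823.
- Direct comparison at 0.05/8 (critical z 2.734): Φ(0.15/0.0453 − 2.734) = Φ(3.308 − 2.734) = 0.72, and Φ(1.822 − 2.734) = 0.18.
- Mean over the cluster: the difference falls to 0.15/3 = 0.05 and the SE to SE/√3. At 0.05/4 (critical z 2.498): Φ(1.910 − 2.498) = 0.28, and Φ(1.052 − 2.498) = 0.07.
- Loss: 0.72 − 0.28 = 44 points at ρ = 0.05, and 0.18 − 0.07 = 11 points at ρ = 0.30.

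**Step 2: the reverse case.** Let all three activities in the cluster shift by 15 points, with ρ = 0.30. The cluster mean has power Φ(3 × 1.052 − 2.498) = Φ(0.658) = 0.74. The chance that at least one of the three direct tests is significant, treating them as independent, is 1 − (1 − 0.18)³ = 0.45. Here the cluster score is better.

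**Step 3: simulation.** Assumptions: 8 activities in 3 blocks or 12 in 4; base rates 0.25 to 0.75; between-infant share of latent variance 0.05 or 0.20; within-block day correlation 0.2 or 0.5; arm differences of 10, 15 or 20 points; 150 runs per scenario (Monte Carlo SE about 4 points). All comparisons used infant-level values with Bonferroni correction.

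| Scenario | Clustering bundles | Clustering activities |
|---|---|---|
| One or two activities change, whole grid | loses 2 to 75 points | loses 4 to 57 points |
| One or two activities change, 15-point difference | loses 25 to 68 | loses 18 to 57 |
| A whole correlated block shifts | loses 2 to 33 | gains 0 to 30 |

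Example: 8 activities, between-infant share 0.20, block correlation 0.2, one activity shifted by 15 points. Power is 0.49 for direct comparison, 0.19 for clustering bundles and 0.21 for clustering activities.

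A second simulation with a different data model (10 activities, infant SD 0.7 on the logit scale, one activity shifted by 0.8 logit) agreed in direction: 56–62% direct, against 18–21% for clustering days and 14–27% for clustering activities. When the whole mix of bundle types shifted, the methods were similar (25–31% against 20–34%).

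**The case against.** The strongest reply is that the descriptive step already covers activities. Each activity is a 0/1 variable, so its proportion by arm will be tabulated. This stands against one tempting inference, that the plan will leave the reader unable to see which activity differs. It will show raw proportions. It will not show an interval or test that respects the correlation among an infant's 18 days, and by the plan's own order the research question is answered in the later step.

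A second reply is that power is a poor yardstick. The study is exploratory, its size is justified by estimation, RQ1 has no powered hypothesis, and describing which activities occur together is a reasonable aim where little is known. This also stands. It is a reason to keep the clustering, but an estimation goal also favours reporting per-activity estimates with intervals.

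Third, the power figures describe assumed tests and cluster counts, because the plan names neither. The RQ1 text can moreover be read as clustering activities rather than days, and under that reading a cluster score can win when a correlated block shifts. All of this is correct. A reader might infer one fixed power loss from such simulations; the documents support no single figure.

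**Conclusion.** The mismatch holds on the text alone: RQ1 asks about activities, and its only named comparison of arms is on cluster frequency. What is missing is a per-activity arm difference with an interval or test by infant.

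The power argument is secondary and conditional. In every scenario simulated on the assumed grid with one or two activities changed, the cluster comparison had lower power, by about 2 to 75 points. That range depends on the assumed number of activities, base rates, within-infant correlation, effect size, number of clusters and test. The direction can reverse, with a gain of 0 to 30 points for an activity-cluster score, when a correlated block shifts together.

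This is an inexpensive improvement to an exploratory analysis. It does not show that the clustering is wrong or that the trial is compromised.

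**What to change.** In the RQ1 Analysis of Section 10, add for each non-diaper activity the arm difference in the percentage of observed bundles in which it occurred, with a 95% CI. Obtain it from an analysis by infant: GEE with a small-sample correction, a random-intercept logistic model, or infant-level proportions where an activity is rare or nearly universal. Include the birth-weight stratum used in randomisation, and apply Holm or FDR control across activities.

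Keep the hierarchical clustering to describe which activities occur together. Make any comparison of cluster frequency at infant level.

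The cost is a few sentences and one simple model per activity on data already collected. The downsides are a multiplicity correction and less power than a cluster score if a whole block of activities shifts together. The simulations used t-tests on infant-level proportions; the GEE and mixed-model options were not simulated at 25 infants per arm, which is why the small-sample correction and the simpler fallback are included.
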